## **8. BIOSPECIMEN STUDIES AND PROCEDURES**

Please refer to the Correlative Laboratory Manual (CLM) for all sample collection, processing, labeling, and shipping instructions of samples outlined below.

### **8.1 Tissue**

Tissue samples will be stored for future correlative analysis which may include PD-1/PD-L1 expression, tumor mutation burden, RNA and next generation sequencing to evaluate genomic markers once funding is available.

#### **8.1.1 Archival Tissue**

Archival tissue is required if available. Archival tissue should be identified at screening and shipped prior to Cycle 2 Day 1 treatment.

### **8.2 Peripheral Blood Samples**

#### **8.2.1 Plasma for Circulating Tumor DNA and miRNA**

Peripheral blood samples will be collected prior to treatment Cycle 1 Day 1, prior to Cycle 3 Day 1 and at progression. For subjects that discontinue treatment for progression, these samples may be collected at the D30 safety visit. Plasma will be stored for possible ctDNA and miRNA analysis once funding is available.

#### **8.2.2 Whole Blood for Somatic Baseline**

Whole blood samples will be collected prior to treatment Cycle 1 Day 1 and stored for future correlative analysis once funding is available.

### **8.3 Stool for Microbiome**

Stool for microbiome will be collected prior to Cycle 1 Day 1 treatment and stored for correlative analysis once funding is available.

### **8.4 Banking of Leftover Biospecimens**

Subject consent will be obtained to bank any leftover samples collected for study-specific correlative research. Hoosier Cancer Research Network (HCRN) will manage the banked samples. Samples will be coded and banked indefinitely in the Hoosier Cancer Research Network Biorepository and used for future unspecified cancer-related research.

### **8.5 Confidentiality of Biospecimens**

Samples will be identified by the subject's study number assigned at the time of registration to the trial. Any material issued to collaborating researchers will be anonymized and only identified by the subject's study number.

## **9. CRITERIA FOR DISEASE EVALUATION**

RECIST 1.1 criteria will apply to subjects with measurable disease. For patients with non-measurable disease the PCWG3 criteria will be utilized for response assessment. PSA response and progression will also be evaluated per PCWG3 criteria. [9]

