### 2.2 Endpoints

#### 2.2.1 Primary Endpoint

- Evaluate the clinical efficacy as defined by 6-month radiologic progression free survival rate (rPFS).
  - For soft tissue lesions, rPFS is defined as the date of Cycle 1 Day 1 to date of radiologic progression of soft tissue lesions per RECIST 1.1 or death whichever occurs first.
  - For bone lesions, rPFS is defined as the date of Cycle 1 Day 1 to date of progression of bone lesions per PCWG3 criteria or death whichever occurs first.

**NOTE:** the “date of progression” is the earlier date of either of those two possible types of progression.

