#### **5. TREATMENT PLAN**

Eligible patients will be treated with the combination of lenvatinib and pembrolizumab. A cycle equals 21 days and therapy will continue until radiographic progression, intolerable toxicity, or patient/physician wishes to discontinue protocol therapy. A maximum of 35 cycles may be administered. On Day 1, when both pembrolizumab and lenvatinib are administered, patients should take the lenvatinib per their normal routine.

If measurable disease is present, response will be assessed by RECIST 1.1 criteria. For bone only metastases at least 2 new areas of metastases will qualify as progression, and PSA response will be also reported per Prostate Cancer working Group 3 guidelines. Section 7 calendar outlines the schedule for assessments.

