#### **6.4 Protocol Therapy Discontinuation**

In addition to discontinuation from therapy related to toxicities as outlined above, a subject will also be discontinued from protocol therapy and followed per protocol under the following circumstances outlined below. The reason for discontinuation of protocol therapy will be documented on the electronic case report form (eCRF)

- Completion of maximum of 35 cycles of study treatment.
- Documented disease progression per RECIST 1.1 (subjects with measurable disease) or PCWG (subjects without measurable disease). If a subject is receiving clinical benefit (as determined by treating physician), treatment can continue after discussion with sponsor-investigator.
- Site investigator determines a change of therapy would be in the best interest of the subject
- Subject requests to discontinue protocol therapy, whether due to unacceptable toxicity or for other reasons
  - In a subject decides to prematurely discontinue protocol therapy (“refuses treatment”), the subject should be asked if he or she may still be contacted for further scheduled study assessments. The outcome of that discussion should be documented in both the medical records and in the eCRF.
- If protocol therapy (both drugs) is interrupted for  $\geq 42$  days from the expected day of the next treatment. If one drug is permanently discontinued, treatment with the other drug may continue at investigator discretion.

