#### 9.6 Evaluation of Non-Target Lesions

Complete Response (CR)	Disappearance of all non-target lesions and normalization of tumor marker level. All lymph nodes must be non-pathological in size (<10 mm short axis)  Note: If tumor markers are initially above the upper normal limit, they must normalize for a subject to be considered in complete clinical response.
Non-CR/ Non-PD	Persistence of one or more non-target lesion(s) and/or maintenance of tumor marker level above the normal limits
Progressive Disease (PD)	Appearance of one or more new lesions and/or unequivocal progression of existing non-target lesions. Unequivocal progression should not normally trump target lesion status. It must be representative of overall disease status change, not a single lesion increase.

Although a clear progression of “non-target” lesions only is exceptional, the opinion of the site investigator should prevail in such circumstances, and the progression status should be confirmed at a later time by the sponsor investigator.

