### 9.8.2 Radiologic Progression Free Survival (rPFS)

rPFS has two components to its definition. For soft tissue lesions, rPFS will be measured from Cycle 1 Day 1 to date of radiologic progression per RECIST 1.1 or death from any cause, whichever occurs first. For bone lesions (non-measurable disease), rPFS will be measured from Cycle 1 Day 1 to date of progression per PCWG3 criteria [9] or death from any cause, whichever occurs first. Thus, the “date of progression” is the earlier date of either of those two possible types of progression. Subjects who have not progressed will be right-censored at the date of the last disease evaluation.

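### The plan does not determine whether one new bone lesion in a patient with measurable disease is an rPFS event: Sections 9 and 6.4 choose the progression criterion by patient, the rPFS definitions by lesion

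*Combined protocol and SAP*

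**What the plan says.** **Rules that sort by patient**

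- Section 9, opening paragraph: "RECIST 1.1 criteria will apply to subjects with measurable disease". It continues: "For patients with non-measurable disease the PCWG3 criteria will be utilized for response assessment".
- Section 6.4, as a ground for stopping protocol therapy: "Documented disease progression per RECIST 1.1 (subjects with measurable disease) or PCWG (subjects without measurable disease". Treatment may continue after discussion if the treating physician sees clinical benefit.
- Section 5 follows the same pattern. It has RECIST 1.1 where disease is measurable, and then: "For bone only metastases at least 2 new areas of metastases will qualify as progression".

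**Rules that sort by lesion**

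- Section 2.2.1, soft tissue: "date of radiologic progression of soft tissue lesions per RECIST 1.1 or death whichever occurs first". Bone: "For bone lesions, rPFS is defined as the date of Cycle 1 Day 1 to date of progression of bone lesions per PCWG3 criteria". Death counts as an event in this leg too.
- Section 9.8.2, bone: "For bone lesions (non-measurable disease), rPFS will be measured from Cycle 1 Day 1 to date of progression per PCWG3 criteria". Here too, death counts as an event.
- Section 12.2.1 repeats the two legs. Sections 2.2.1 and 9.8.2 add that the earlier of the two progression dates is used.

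**What counts as progression under the RECIST tables**

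- Section 9.6: "Appearance of one or more new lesions and/or unequivocal progression of existing non-target lesions". The target-lesion table in 9.5 and the overall-response table in 9.7 also make any new lesion progressive disease. None of the three excepts bone.
- Section 9.2 lists bone lesions as non-measurable lesions within that same system.

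**The concern.** The two ways of sorting meet in a patient who has both measurable soft-tissue disease and bone metastases. When the only change on a scan is one new bone lesion, the patient-based rule leads to the RECIST tables, where a single new lesion is progression. The lesion-based rule refers the lesion to PCWG3, whose bone threshold the protocol does not reproduce for this kind of patient.

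The primary endpoint is binary (rPFS of at least 6.00 months, yes or no) and the decision rests on small counts: 3 successes in 27 to continue, 7 in 40 to call the treatment promising. A rule that sites can read in two ways feeds directly into those counts.

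Follow-up adds to the problem. Under footnote 5 of the study calendar, scheduled imaging runs until the patient is off study therapy. A patient taken off as progressed under Section 6.4 therefore leaves the imaging schedule. If the lesion does not also count under the bone rule, status at 6 months may be uncertain.

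**Working it through.** **1. One case traced through each section.** Take a patient with a measurable lymph node that is stable, and one new bone lesion at a scheduled scan before 6 months.

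| Section | How the criterion is chosen | Result for this scan |
|---|---|---|
| 9 (opening) | Patient has measurable disease, so RECIST 1.1 | Go to 9.5 to 9.7 |
| 9.5, 9.6, 9.7 | Any new lesion, bone not excepted | Progression |
| 6.4 | Patient has measurable disease, so RECIST 1.1 | Progression, a ground for stopping therapy |
| 5 | At least 2 new areas, bone-only disease | Does not apply to this patient |
| 2.2.1, 12.2.1 | RECIST progression limited to soft tissue lesions; bone by PCWG3 | Depends on PCWG3, not reproduced |
| 9.8.2 | As above, but the soft-tissue leg does not repeat the soft-tissue limit after the word progression | Open to either reading |

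The last row matters because 9.8.2 sits under the patient-based opening rule of Section 9 and takes the earlier date. One site could count the bone lesion as RECIST progression; another could refer it to PCWG3. Both would be following the text.

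**2. What happens next.** If progression is regarded as documented, Section 6.7 provides survival follow-up. If it is not, imaging after stopping is at the site investigator's discretion (Section 6.7; study calendar, footnote 5). Section 9.8.2 censors patients without progression at the last disease evaluation, which may fall before 6 months. Section 12 does not say how such a patient is scored on the yes/no endpoint.

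**3. The plan's own design figures.** Inputs from Section 12.3: N1 = 27, R1 = 2, N = 40, R = 6, p0 = 0.10, p1 = 0.25, alpha limit 0.125, power 0.90.

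- PET = P(X ≤ 2), X ~ Bin(27, 0.10) = 0.4846 (stated 0.485).
- ASN = 27 + (1 − 0.4846) × 13 = 33.70 (stated 33.70).
- Probability of a positive result at success rate p: the sum over x = 3 to 27 of P(X1 = x) × P(X2 ≥ 7 − x), with X1 ~ Bin(27, p) and X2 ~ Bin(13, p).
- At p = 0.25 this is 0.900 (stated 0.90). At p = 0.10 it is 0.098, within the 0.125 limit.

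The design reproduces, and this point does not dispute it.

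**4. Illustration of size.** Assume a share f of patients who would otherwise be 6-month successes is scored as progressed solely because of one new bone lesion. The success rate at the alternative is then 0.25 × (1 − f).

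| f | Success rate | Power |
|---|---|---|
| 0 | 0.2500 | 0.900 |
| 5% | 0.2375 | 0.866 |
| 10% | 0.2250 | 0.822 |
| 20% | 0.2000 | 0.708 |

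The documents give no value for f. It covers only patients with no other progression and no death by 6 months, so it could be small.

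**The case against.** The best reply is that the endpoint is already defined. All three rPFS definitions are lesion-based, and two of them say how the legs combine. Section 6.4 concerns stopping therapy, and Section 9 assigns PCWG3 in a sentence about response assessment. On this view a careful reader would apply the lesion rule and the rest is loose wording.

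Part of this stands. A reader might infer that the lesion is both progression and not progression for the primary endpoint. The documents do not support that. The endpoint is under-determined for this patient, not defined twice in opposite ways. The not-progression half would also need a PCWG3 threshold above one lesion, which the documents write out only for bone-only disease.

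A reader might also infer that the later rPFS event is never looked for. That is too strong. Treatment, and with it scheduled imaging, may continue after progression if there is clinical benefit; discretionary scans are recorded when available; death remains an event. What ends at discontinuation is imaging on schedule.

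Finally, a reader might claim inflated type I error. If p0 = 0.10 had been set under the stricter rule and the looser rule were applied with f = 10%, the null success rate would be 0.10/0.90 = 0.111 and the chance of a positive result 0.147, above 0.125. But the documents do not show which rule lies behind p0, so this is not a finding.

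The reply still does not remove the ambiguity. Section 9.8.2 lies under the patient-based rule and drops the soft-tissue limit at the point where it matters, the RECIST tables do not except bone, and no section says which rule prevails.

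**Conclusion.** Wrong as written: the sections give conflicting rules that bear on the primary endpoint. For a patient with measurable disease, the documents do not determine whether or when one new bone lesion is an rPFS event.

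That conclusion rests on the text alone and needs no assumption about frequency. Nor does the sensitivity of the decision: 7/40 is promising and 6/40 is not, 3/27 continues and 2/27 stops, so one patient can change either outcome. The power figures are different in kind. They show what various shares of reclassified successes would do and are not an estimate of what will happen in this trial. The sample size calculation is unaffected.

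**What to change.** For the rPFS endpoint:

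1. State one rule in Section 9.8.2 and refer to it from Sections 2.2.1, 9 and 12.2.1: every patient is assessed by both criteria, soft tissue by RECIST 1.1 and bone by PCWG3, and the earlier progression date is used.
2. In the soft-tissue leg of 9.8.2, restore after the word progression the limit to soft tissue lesions that 2.2.1 and 12.2.1 carry.
3. State that, for rPFS, a new bone lesion is dated only under the bone rule, including in patients with measurable disease.

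The progression wording in Sections 5 and 6.4 governs treatment. The sponsor must reconcile it with the endpoint rule; no treatment rule is proposed here.

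The cost is a few sentences in an amendment. No scans are added, because the calendar already schedules bone scans with the CT or MRI assessments.

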### **9.1 Measurable Disease**

Measurable disease is defined as the presence of at least one measurable lesion. Measurable lesions are defined as those that can be accurately measured in at least one dimension (longest diameter to be recorded) as  $\geq 20$  mm by chest x-ray, as  $\geq 10$  mm with CT scan, or  $\geq 10$  mm with calipers by clinical exam. All tumor measurements must be recorded in millimeters (or decimal fractions of centimeters).

#### **9.1.1 Malignant Lymph Nodes**

To be considered pathologically enlarged and measurable, a lymph node must be  $\geq 15$  mm in short axis when assessed by CT scan (CT scan slice thickness recommended to be no greater than 5 mm). At baseline and in follow-up, only the short axis will be measured and followed.

### **9.2 Non-measurable Lesions**

All other lesions (or sites of disease), including small lesions (longest diameter  $<10$  mm or pathological lymph nodes with  $\geq 10$  to  $<15$  mm short axis), are considered non-measurable disease. Bone lesions, leptomeningeal disease, ascites, pleural/pericardial effusions, lymphangitis cutis/pulmonitis, inflammatory breast disease, and abdominal masses (not followed by CT or MRI), are considered as non-measurable.

**NOTE:** Cystic lesions that meet the criteria for radiographically defined simple cysts should not be considered as malignant lesions (neither measurable nor non-measurable) since they are, by definition, simple cysts. ‘Cystic lesions’ thought to represent cystic metastases can be considered as measurable lesions, if they meet the definition of measurability described above. However, if non-cystic lesions are present in the same subject, these are preferred for selection as target lesions.

### **9.3 Target Lesions**

All measurable lesions up to a maximum of 2 lesions per organ and 5 lesions in total, representative of all involved organs, should be identified as target lesions and recorded and measured at baseline. Target lesions should be selected on the basis of their size (lesions with the longest diameter), be representative of all involved organs, but in addition should be those that lend themselves to reproducible repeated measurements. It may be the case that, on occasion, the largest lesion does not lend itself to reproducible measurement, in which circumstance the next largest lesion which can be measured reproducibly should be selected. A sum of the diameters (longest for non-nodal lesions, short axis for nodal lesions) for all target lesions will be calculated and reported as the baseline sum diameters. If lymph nodes are to be included in the sum, then only the short axis is added into the sum. The baseline sum diameters will be used as reference to further characterize any objective tumor regression in the measurable dimension of the disease.

#### 9.4 Non-target Lesions

All other lesions (or sites of disease) including any measurable lesions over and above the 5 target lesions should be identified as non-target lesions and should also be recorded at baseline. Measurements of these lesions are not required, but the presence, absence, or in rare cases unequivocal progression of each should be noted throughout follow-up.

#### 9.5 Evaluation of Target Lesions

**NOTE:** In addition to the information below, also see the international criteria proposed by the Response Evaluation Criteria in Solid Tumors (RECIST) Committee, version 1.1[8] (Eur J Cancer 45;2009:228-247) for special notes on the assessment of target lesions.

Complete Response (CR)	Disappearance of all target lesions. Any pathological lymph nodes (whether target or non-target) must have reduction in short axis to <10 mm.
Partial Response (PR)	At least a 30% decrease in the sum of the diameters of target lesions, taking as reference the baseline sum diameters
Progressive Disease (PD)	At least a 20% increase in the sum of the diameters of target lesions, taking as reference the smallest sum on study (this includes the baseline sum if that is the smallest on study). In addition to the relative increase of 20%, the sum must also demonstrate an absolute increase of at least 5 mm. (Note: the appearance of one or more new lesions is also considered progressions).
Stable Disease (SD)	Neither sufficient shrinkage to qualify for PR nor sufficient increase to qualify for PD, taking as reference the smallest sum diameters while on study

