4: Chromogranin A, neuron specific enolase and urine NTx (optional) will be performed at screening/day 1 then prior to treatment every other Cycle starting at Cycle 3 Day 1 then at the D30 safety visit. PSA should be obtained at screening then prior to treatment every Cycle then at the D30 safety visit. Subjects that come off study without progression should have PSA obtained per investigator discretion. Testosterone will be performed at screening and at the D30 safety visit.

5: Tumor response assessment will consist of evaluation by CT scans of chest and MRI or CT of abdomen and pelvis. If a PET/CT is done for tumor assessment and if tumor/s are visible on the CT, this may be used for tumor evaluation. A bone scan will be obtained at screening and with other radiology imaging at the frequency as outlined below. An MRI of the brain should be performed at screening if there is a concern for the presence of brain metastases. Tumor imaging will be done at screening and every 3 cycles (9 weeks) for the first 12 cycles (36 weeks) and then every 4 cycles (12 weeks) until the patient is off study therapy (window of  $\pm$  1 week). Tumor imaging should follow week intervals in the case of study treatment delays due to toxicities. During follow up after completion of study treatment, imaging frequency is at the discretion of the site investigator. Imaging selected for each subject should remain the same throughout the study. Tumor imaging to be done at treatment discontinuation/safety follow up visit is at discretion of site investigator. If tumor assessments are available for subjects who have not yet experienced progressive disease (PD) at the time treatment is discontinued, the follow-up tumor evaluations will be documented in the eCRF until PD or death is confirmed, or until another treatment is initiated.

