## 9.8 Definitions for Response and Survival Evaluation

### 9.8.1 Time to Response (TTR)

The time between initiation of therapy and first documentation of PR or CR.

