#### **9.8.4 Duration of Response (DoR)**

DoR will be measured from the start date of the best response achieved until the date of relapse (i.e., progression). Continuing responders will be right-censored as of the most recent date on which their response status had been assessed. DoR applies to only the patients who achieve either a complete response (CR) or a partial response (PR).

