### 12.2.2 Definition of Secondary Endpoints

- Safety of the combination will be assessed based on NCI Common Terminology Criteria for Adverse Events (CTCAE) version 5.0.
- Overall survival (OS) will be measured from Cycle 1 Day 1 to date of death from any cause. OS is further defined (including its censoring) in Section 9.8.3.
- ORR will be the proportion of patients achieving either a complete response (CR) or a partial response (PR), among all patients meeting the criteria of Section 12.6, as well as among all patients enrolled.
- DoR will be measured from the start date of the best response achieved until the date of relapse (i.e., progression). DoR is further defined (including its censoring) in Section 9.8.4. DoR applies to only the CR or PR patients.

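### As written, a CR or PR on one scan counts towards ORR and starts DoR; ORR and DoR should be reported both unconfirmed and confirmed

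*Combined protocol and SAP*

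**What the plan says.** - Section 9.5 sets PR by one comparison with baseline: "At least a 30% decrease in the sum of the diameters of target lesions, taking as reference the baseline sum diameters". The table in Section 9.7 combines target, non-target and new-lesion status into an overall response without calling for a second assessment.
- Section 12.2.2 states: "ORR will be the proportion of patients achieving either a complete response (CR) or a partial response (PR". It gives two denominators: patients evaluable under Section 12.6, and all patients enrolled. Section 12.4.2 analyses ORR like the 6-month rPFS rate, so it gets a point estimate and a Wilson 95% interval (Section 12.4.1), with no test or threshold.
- Time to response (Section 9.8.1) is "The time between initiation of therapy and first documentation of PR or CR". For duration, Section 9.8.4 says "DoR will be measured from the start date of the best response achieved until the date of relapse".
- The only confirmation step in the response criteria is in Section 9.6, "the progression status should be confirmed at a later time by the sponsor investigator". It concerns non-target progression, not response.
- Section 9 applies RECIST 1.1 to measurable disease, and Section 9.5 points to it "for special notes on the assessment of target lesions". Neither place states a confirmation rule for CR or PR.
- Footnote 5 of the study calendar schedules imaging "every 3 cycles (9 weeks) for the first 12 cycles (36 weeks) and then every 4 cycles (12 weeks" until study therapy ends. Section 5 adds: "A maximum of 35 cycles may be administered".

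**The concern.** Without a repeat requirement, ORR records whether any of a patient's readings fell to or below the 30% line. A patient with stable disease close to that line has a fresh chance at each scan of being read as a responder, whereas a true responder needs only one qualifying reading to be counted. The two kinds of error therefore do not balance. There is no control arm in which the same error would cancel, and no central image review is described.

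ORR and DoR are two of the four secondary objectives, and clinical response is also an outcome in the exploratory marker models (Section 12.4.3). Because the plan does not say whether response is confirmed, two analysts could take different responder sets from the same data. A choice made after the data are seen would be data-driven.

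**Working it through.** **1. Figures in the plan.** No target or precision is stated for ORR. The design that supplies the progression rates reproduces: the probability of at most 2 successes in 27 at p = 0.10 is 0.485; ASN = 27 + (1 − 0.4846) × 13 = 33.70; power at p = 0.25 is 0.900.

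**2. Number of looks.** Scans fall at cycles 3, 6, 9, 12, 16, 20, 24, 28 and 32 (weeks 9 to 96), so nine is the maximum within 35 cycles. To see how many occur before progression, assume exponential rPFS with λ = −ln(p)/26.09 per week and S(w) = exp(−λw).

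| 6-month rPFS | λ | reach scan 1 | scan 2 | scan 3 | scan 4 | scan 9 | mean scans |
|---|---|---|---|---|---|---|---|
| 10% | 0.0883 | 45% | 20% | 9% | 4% | 0.02% | 0.81 |
| 25% | 0.0531 | 62% | 38% | 24% | 15% | 0.6% | 1.55 |

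**3. One patient.** Take a constant true shrinkage of 20% (stable disease) and independent log-scale error σ at baseline and at each scan (assumed). On one scan, P(read as PR) = Φ[(ln 0.70 − ln 0.80)/(σ√2)] = Φ[−0.1335/(σ√2)].
- σ = 0.05: Φ(−1.89) = 0.029. σ = 0.10: Φ(−0.94) = 0.173.
- At least one PR reading in two scans (simulated, because the baseline error is shared): 0.053 and 0.275.
- PR on both scans: 2 × 0.029 − 0.053 = 0.005, and 2 × 0.173 − 0.275 = 0.071.

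**4. Whole trial, model A.** This simulates 200,000 patients. Assumed: true best change with mean −10% and SD 25%; exponential progression as in step 2, independent of depth of response; follow-up ended by a measured 20% rise over nadir; every patient has target lesions. *True* means a real shrinkage of at least 30% in a patient still progression-free at week 9. Entries are percentages of all patients.

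| 6-month rPFS | error | true | unconfirmed | excess | confirmed at next scan | shortfall |
|---|---|---|---|---|---|---|
| 10% | 5% | 9.5 | 10.4 | 0.9 | 4.0 | 5.5 |
| 10% | 10% | 9.6 | 12.0 | 2.4 | 3.8 | 5.8 |
| 25% | 5% | 13.3 | 15.1 | 1.8 | 8.0 | 5.3 |
| 25% | 10% | 13.1 | 17.4 | 4.3 | 7.4 | 5.7 |

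The asymmetry is visible in the last row. False responders were 5.6 points; true responders missed were 13.1 − (17.4 − 5.6) = 1.3 points; the net is 4.3. At 15% error the excess would be 13.7 − 9.6 = 4.1 and 20.2 − 13.1 = 7.1 points.

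**5. Model B.** Here the true nadir is held for two scans and slow regrowth follows, with an added constant hazard that brings progression-free status at week 27 to the design rates. At 25%, unconfirmed ORR is about 1.5 to 6 points high and confirmed ORR about 1.5 to 4 low. At 10%, the figures are about 1 to 3.5 high and 2.5 to 4.5 low.

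**6. Scale.** Across both models, with error of 5% to 10%, the excess is about 1 to 6 points. In 40 patients that is 0.4 to 2.4 responders if all have measurable disease, and proportionally fewer otherwise. For comparison, the Wilson 95% interval for 6/40 is 7.1% to 29.1%, a half-width of 11 points.

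**The case against.** The strongest reply is that the documents never say a single scan suffices. They are silent, and they invoke RECIST 1.1. What that source requires in a trial of this kind cannot be checked from the documents. This stands as a limit on the claim: the plan does not adopt a single-scan rule in terms. It does not close the gap, because an analyst following the protocol's own definitions finds no second-scan condition.

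A reader might infer that ORR is the best of nine noisy readings. Nine is correct only as a ceiling. At the design rates the mean is about one or two scans before progression, and fewer than one patient in four reaches a third. The upward tendency does not depend on nine looks, but its size does depend on how many occur.

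A reader might also infer that ORR should be confirmed only. The calculations do not support that as the sole headline: next-scan confirmation fell below the true rate in both models. The shortfall is largest in model A, where progression is unrelated to depth of response. It is smaller when responders progress more slowly.

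It is also true that Section 3.1 requires only radiologic evidence of metastases, and that Sections 5 and 9 provide for bone-only or non-measurable disease. Such patients cannot produce a false 30% shrinkage.

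**Conclusion.** The gap is real, modest in consequence and cheap to close. On the text as it stands, one qualifying scan makes a responder, and the resulting error in ORR tends upward. The size, roughly 1 to 6 points among patients with measurable disease, rests on an assumed per-scan error of 5% to 10%, assumed distributions of tumour change, and the design's rPFS rates. The documents give neither an error figure nor the measurable-disease fraction, so overstatement of a particular size is not established. It is a systematic component that the Wilson interval does not cover, though smaller than that interval's half-width. For DoR, the set of patients changes, but this check does not settle the direction of the effect.

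A reader might take this as a threat to the trial's conclusion. The documents do not support that: ORR is secondary and descriptive, and the sample size and both decision thresholds in Section 12.3 use 6-month rPFS only.

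**What to change.** In Sections 9.7, 9.8.4 and 12.2.2 (and 2.2.2, to match), state that:
- ORR will be reported as unconfirmed (any CR or PR) and as confirmed (criteria met again at the next scheduled scan, with the response dated from the first of the two scans), each with its Wilson 95% interval and for both existing denominators;
- DoR will be reported for both responder sets;
- responders with no later scan will be listed separately from those whose response was not reproduced.

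Settle this before the response data are read.

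The cost is a little more analysis. No scans are added, because the calendar already supplies the next one, 9 or 12 weeks later, for patients still on therapy. After treatment stops, imaging is at the site investigator's discretion (Section 6.7 and calendar footnote 5), which is why the no-later-scan group needs its own line. The confirmed figure will be somewhat low because some true responders progress or stop before the next scan. The two figures should be read together.
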